1.2. Primary Endpoints: Primary Study Hypotheses

For this study, the primary efficacy and primary safety endpoint will be considered as co-primary endpoints. That is, both primary efficacy and safety endpoint need to be significant to claim the study as successful.

1.2.1. Primary Efficacy Endpoint

The Primary Efficacy endpoint is the *primary patency* of the VENOVO™ Venous Stent (BVS) at 12 months post index procedure, which need to be better than the Performance Goal (PG) (74%) developed from the patency of other marketed stents at 12 months (see section 6.4 sample size consideration for the derivation of the PG).

The primary efficacy endpoint will be evaluated by the following hypothesis:

- H₀: The primary patency rate at 12 months post index procedure from the overall VENOVO™ Venous Stent (BVS) patients (PTS and NIVL combined) is at most as good as that of the PG;
H_a: The primary patency rate at 12 months post index procedure from the overall VENOVO™ Venous Stent (BVS) patients (PTS and NIVL combined) is better than that of the PG;

$$H_0: 0.45 \times \pi_{NIVL} + 0.55 \times \pi_{PTS} \leq PP_{PG} \text{ v.s } H_a: 0.45 \times \pi_{NIVL} + 0.55 \times \pi_{PTS} > PP_{PG}$$

Where π_{PTS} is the true primary patency rate at 12-month post index procedure for PTS patients, π_{NIVL} is the true primary patency rate at 12-month post index procedure for NIVL patients, and $PP_{PG}=74\%$. The test statistics can be formulated as:

$$Z = \frac{0.45 \times p_{NIVL} + 0.55 \times p_{PTS} - 0.74}{\sqrt{\frac{(0.45)^2 \times PG_{NIVL}(1 - PG_{NIVL})}{n_{NIVL}} + \frac{(0.55)^2 \times PG_{PTS}(1 - PG_{PTS})}{n_{PTS}}}}$$

Where p_{PTS} and p_{NIVL} are observed primary patency rate at 12-month post-index procedure for PTS and NIVL patients, respectively. PG_{PTS} ($=77\%-10\%=67\%$) and PG_{NIVL} ($=93\%-10\%=83\%$) are expected value for PTS and NIVL patients under the null; n_{PTS} and n_{NIVL} are the number of PTS and NIVL patients in the analysis. A one-sided p-value will be calculated using a normal distribution. The study device will be considered to have achieved the primary efficacy objective if the one-sided p-value is less than 0.05.

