1.4. Sample Size Consideration

Primary Efficacy Endpoints:

Table 6.3-1 shows the possible combinations of proportions of patients that could be enrolled in the study along with the weighted mean primary patency (PP) and the sample size required for 85% power against the PG (PP_{PG}).

Bard has chosen the sample size for the trial required for 85% power when the proportion of NIVL patients with endpoints is 20% and the proportion of PTS patients is 80%. This is the company's best guess for the actual enrollment. The estimate from the literature of the PP is 80% (used as the alternative proportion in the sample size estimate) and the PP_{PG} is 70% (used as the null proportion). The sample size is 138 patients. (This row is highlighted in yellow in Table 1.3-1.). With 45:55 split of the sample size, the PP_{PG} becomes 74%. As indicated in Table 6.3-1, the sample size required for 85% power will be between 121 and 125, which is less than planned sample size 138. In other words, with the same sample size as planned, >85% power can be achieved.

All sample size estimates in Table 1.3-1 were made with PASS 12 (Hintze, J. (2013). PASS 12. NCSS, LLC. Kaysville, Utah, USA. www.ncss.com) using the Fisher's Exact Binomial test for one proportion.

Note that the sample size of 138 patients is the number of evaluable patients. Up to 170 patients may be enrolled, depending on the losses-to-follow-up, deaths, and study withdrawals. Bard further estimates that approximately 50% of consented subjects will not meet the eligibility criteria (i.e., will

be Screen Failures), and therefore will not be enrolled in the study. The estimated consented population will therefore be 340 ($170/.5 = 340$).

Table 1.3 -1. Estimates of the Sample Size Based on the Proportions of NIVL and PTS Subjects in the Clinical Trial

NIVL %	PTS %	Weighted Mean PP	α	Performance Goal (PP _{PG})	Sample Size of BVS for 85% Power
5%	95%	77.9%	5%	68%	146
10%	90%	78.7%	5%	69%	140
20%	80%	80.4%	5%	70%	138
30%	70%	82.0%	5%	72%	132
40%	60%	83.6%	5%	74%	125
50%	50%	85.2%	5%	75%	121
60%	40%	86.9%	5%	77%	112

Primary Safety Endpoint:

The freedom-from-MAE rate estimated from the literature was 99%, which was used as the alternative proportion. The null proportion was the M_{PG} of 89%. With 42 BVS subjects, the study will have 85% power to detect a difference, and with 138 BVS subjects, the study power will be over 99%.

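### The primary efficacy hypothesis is worded for the overall patients but tests a rate fixed at 45% NIVL and 55% PTS, so at another mix a success does not show overall patency above 74%

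*Combined protocol and SAP*

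**What the plan says.** Section 1.2.1 states the primary efficacy hypothesis twice. In words, the alternative is that the 12-month primary patency rate "from the overall VENOVO™ Venous Stent (BVS) patients (PTS and NIVL combined) is better than that of the PG". In symbols, the tested quantity is 0.45 times the NIVL rate plus 0.55 times the PTS rate, against a fixed goal of 74%. The Z statistic uses the same fixed weights. The two group sizes, which "are the number of PTS and NIVL patients in the analysis", enter only its variance. The decision rule is: "The study device will be considered to have achieved the primary efficacy objective if the one-sided p-value is less than 0.05".

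Section 1.4 sizes the trial for "85% power when the proportion of NIVL patients with endpoints is 20% and the proportion of PTS patients is 80" percent, and says of that mix: "This is the company's best guess for the actual enrollment". The goal there is 70%. The same paragraph then says that the goal becomes 74% at a 45:55 split. Table 1.3-1 likewise lets the goal move with the mix.

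No text calls the tested quantity a standardised rate. None says how a success should be read if the analysed mix is not 45:55.

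**The concern.** The worded hypothesis reads as a statement about the patients in the study. The formula is a statement about a reference population with 45% NIVL. These are different quantities unless the analysed mix is near 45:55 or both groups have the same patency. The plan expects unequal patency (93% NIVL, 77% PTS in section 1.2.1), and its stated best guess for enrollment is far from 45:55.

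Primary patency is one of two co-primary endpoints that must both succeed (section 1.2). If the success claim is taken from the words, the trial could report that overall patency exceeds 74% when the test has not shown it.

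**Working it through.** **Inputs.** From section 1.2.1: weights 0.45 and 0.55; goal 74%; literature rates 93% (NIVL) and 77% (PTS); null rates 83% and 67%; one-sided 5%, normal approximation. From section 1.4: 138 evaluable patients; mixes 20:80 (goal 70%) and 45:55 (goal 74%). At 20:80, 0.20 × 138 = 27.6, taken as 28 NIVL and 110 PTS.

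**1. The plan's sample size.** For an exact one-sided binomial test of 70% against 80% at 5%, the smallest n with at least 85% power is 138 (power 85.1%, actual alpha 4.7%). The plan's figure reproduces.

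**2. Where the two goals come from.**
- 45:55: 0.45 × 83% + 0.55 × 67% = 74.2%.
- 20:80: 0.20 × 83% + 0.80 × 67% = 70.2%.

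The 74% and 70% goals are the same pair of group goals at two mixes.

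**3. Tested rate against the rate in the analysed patients.** With NIVL share s, the difference is (0.45 − s) × (NIVL rate − PTS rate). At the literature rates:
- tested: 0.45 × 93% + 0.55 × 77% = 84.2%;
- in the analysed patients at 20:80: 0.20 × 93% + 0.80 × 77% = 80.2%;
- difference: (0.45 − 0.20) × 16 = 4.0 points.

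**4. Pass line at 28/110.** SE = √(0.45² × 0.83 × 0.17/28 + 0.55² × 0.67 × 0.33/110) = 0.0404. The test succeeds when the weighted rate exceeds about 0.74 + 1.645 × 0.0404 = 80.6%.

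**5. Size for the formula's own hypothesis at 28/110.** Two independent binomials were enumerated exactly through the Z statistic. Rejection is 5.2% at 83%/67%, and 4.7% when the 45:55 rate is exactly 74% at a 16-point gap. The test is sound for the quantity in the formula.

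**6. Chance of success when the overall rate is exactly 74%, so that the worded null is true.** Same enumeration. The 16-point gap is the plan's own (93 − 77 and 83 − 67).

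| Mix (NIVL/PTS) | Gap, NIVL − PTS | Probability of success |
|---|---|---|
| 20:80 (28/110) | 0 | 6% |
| 20:80 | 5 points | 10% |
| 20:80 | 10 points | 15% |
| 20:80 | 16 points (about 87%/71%) | 25% |
| 20:80 | 20 points (about 90%/70%) | 33% |
| 20:80 | about 24 points (93%/69.2%) | 43% |
| 30:70 (41/97) | 16 points | 16% |
| 40:60 (55/83) | 16 points | 7.6% |
| 45:55 (62/76) | 16 points | 4.6% |
| 60:40 (83/55) | 16 points | 1.2% |

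With 170 analysed at 20:80 (34/136) and a 16-point gap, the probability is 28%. Above 45% NIVL the mismatch works against success.

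**7. One sample that would pass.** With 26/28 NIVL and 78/110 PTS patent, the weighted rate is 0.45 × 26/28 + 0.55 × 78/110 = 80.8%, Z = 1.68, p = 0.046: a success. The overall rate is 104/138 = 75.4%, and an exact one-sided test of it against 74% gives p = 0.40.

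**The case against.** The strongest reply is that the formal hypothesis is unambiguous. The symbols follow the words directly, both parameters are defined, and the statistic and success rule are fixed, so two analysts would reach the same decision. The worded phrase can be read as shorthand for the combined rate on the next line. This stands as a defence of the decision rule.

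A reader might infer that the trial's false-positive rate is 25% or even 43%. The documents do not support that. In those scenarios both groups exceed their own null rates (87% against 83% and 71% against 67% at the 16-point gap), and the 45:55 rate is truly above 74%. The overall 74% also exceeds the plan's 70% goal for a 20:80 mix. Rejecting the formula's null is then correct. The 43% is also the top of the range: it puts NIVL at its full literature rate and PTS about 8 points below its own.

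A reader might also infer that the trial will be analysed at 20:80. Section 1.4 calls that mix the best guess, but the same paragraph carries 45:55, and the documents do not settle which is expected. At 45:55 the problem disappears.

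Nor does any text say that the weighted figure will be the published headline rate, and the overall rate can be recovered from the inputs to Z. Passes with observed overall patency at or below 74% are possible but uncommon: under 5% in the 28/110 scenarios above.

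What remains is that the words and the formula name different quantities, that nothing tells the reader which one a success concerns, and that the plan itself anticipates a mix at which they diverge.

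**Conclusion.** The mismatch is real and should be corrected, as an error in what a primary success may be said to show. The decision rule is not at fault. The unsupported statement is specifically that overall patency is above 74%.

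The 25% figure assumes an analysed mix of 28/110, a 16-point gap and a true overall rate of exactly 74%. It falls to 6% with no gap, and to about 5% at 45:55 whatever mix was guessed beforehand. If the device performs at the literature rates, the tested rate would be about 4 points above the rate in the analysed patients at 20:80.

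**What to change.** - Keep the test statistic, the 74% goal and the success rule.
- Reword the null, the alternative and the success claim in section 1.2.1 as the 12-month primary patency rate standardised to 45% NIVL and 55% PTS.
- State that the 74% goal applies only to that standardised rate.
- Pre-specify, beside it, the unweighted 12-month patency of the analysed ITT patients with an exact 95% confidence interval, labelled as the observed overall rate.
- Reconcile the 20:80 and 45:55 statements in section 1.4, so that it is clear which mix is expected and which one sets the goal.

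Replacing the test with an unweighted one against a fixed 74% would be a poor repair. At 28/110 and the literature rates its power is 53%, against 88% for the planned test, because the goal would no longer match the mix. Against the 70% goal the unweighted test has 87% power.

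The cost is SAP wording and one descriptive estimate from data already collected. The downside for the sponsor is presentational: with few NIVL patients, the observed overall rate beside the primary result will look about 4 points less favourable.

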1.2.2. Primary Safety Objective

The primary safety endpoint of the study is freedom from major adverse events (MAEs) and freedom from TVR through 30 days post-index procedure, as adjudicated by a Clinical Events Committee (CEC). The performance goal of free from primary safety event is 89%.

The primary safety endpoint will be evaluated by the following hypothesis: H_0 : The primary safety endpoint absence from event rate in the VENOVO™ Venous Stent (BVS) through 30 day at most as large as that of the PG;

H_a : The primary safety endpoint absence from event rate in the VENOVO™ Venous Stent (BVS) through 30 day is better than that of the PG;

$$H_0: M_{BVS} \leq M_{PG} \quad H_a: M_{BVS} > M_{PG}$$

Where $M_{PG}=89\%$ A one-sided p-value will be derived based on an exact binomial test. The study device will be considered to have achieved the primary safety objective if the one-sided p-value is less than 0.05.

1.2.3. Handling of Missing Data

Study endpoints may be missing due to withdrawal of consent, investigator's decision to terminate, lost to follow-up and death. As long as the missing data is unrelated to the study intervention and the observed and unobserved data, limiting the analysis to those subjects who contribute endpoints produces unbiased estimates of the event rates.

The *reason* for missing data in any subject will be reported. If there is any indication that missing data is related to the study intervention, a worst-case analysis may be performed in addition to the standard analysis. In a worst-case analysis, a failure of effectiveness or safety will be assumed to have occurred at the time the subject was censored.

In addition, regardless of whether missing data are related to the study intervention, a tipping-point analysis will be performed, in which assumptions about missing data are varied from worst-case to best-case to examine at what point the missing data would alter the results of the analysis.

Multiple imputation will also be explored as another method to handle missing data.

1.2.4. Assessment of Poolability of Sites

The sites will be tested for potential differences in the primary endpoint. Sites with fewer than 10 treated subjects will be combined for this purpose. The pooling will be restricted within country. The sites with less than 10 treated subjects will be sorted by site number within each country and pooled by order to form one or more combined site(s) with at least 10 treated subjects. A logistic regression analysis will be performed with sites as a fixed effect. If the p-value associated with the sites effect is < 0.15 , it will be considered as evidence of statistical significance.

If there are any site effects, the sites that have similar and dissimilar results will be grouped and exploratory analyses will be performed to investigate the potential reason for the differences among sites.

An analysis will be performed to examine the potential difference in the primary endpoint between the two geographic regions (US vs. OUS). A logistic regression model will be fit that includes fixed effect for geography. If the p-value of the geography effect is < 0.15 , it will be considered evidence of a statistically significant difference between the geographic regions, and additional analyses will be performed to explore the differences between geographies to assess their potential causes and whether or not they are clinically meaningful.

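### The US/OUS poolability model names no PTS/NIVL term, so if the regional mixes differ markedly its p<0.15 flag partly reflects case mix and can hide a true deficit in the high-NIVL region

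*Combined protocol and SAP*

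**What the plan says.** SAP section 1.2.4 sets up two separate screens, each flagged at p<0.15.

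- **Geography.** "A logistic regression model will be fit that includes fixed effect for geography". No other term is named. If the flag fires, "additional analyses will be performed to explore the differences between geographies to assess their potential causes", and their clinical meaning is considered.
- **Sites.** "A logistic regression analysis will be performed with sites as a fixed effect". Small sites are grouped first: "Sites with fewer than 10 treated subjects will be combined for this purpose", within country, until each group has at least 10. A site effect leads to exploratory work on its reasons. The type of test (likelihood-ratio, Wald or score) is not named.

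Section 1.2.1 takes the two disease groups to have different patency. The null rates of 83% (NIVL) and 67% (PTS) "are expected value for PTS and NIVL patients under the null", each obtained by taking 10 points off 93% and 77%. The primary Z weights the observed rates 0.45 (NIVL) and 0.55 (PTS), and its variance uses the two counts, which "are the number of PTS and NIVL patients in the analysis". Every analyzed subject must therefore already be classified as PTS or NIVL.

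Section 1.2.4 refers to the primary endpoint in the singular, although section 1.2 has two co-primaries. This note takes patency to be meant.

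**The concern.** By the SAP's own figures, disease group is a strong determinant of 12-month patency, yet the regional comparison is specified without it. A difference in case mix between the US and elsewhere then appears as a difference between regions.

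The two directions of error do not matter equally. A flag caused by case mix leads to an exploratory step in which PTS/NIVL is an obvious thing to examine, so it can be explained. A real regional deficit that is partly offset by a favorable mix is less likely to reach that step at all, because the exploration is conditional on the flag. What is at stake is which regional differences get followed up.

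**Working it through.** **Inputs from the SAP.** Patency 93% NIVL and 77% PTS (1.2.1); flag at p<0.15 (1.2.4); 138 evaluable subjects (1.4). **Assumptions.** A 90/48 regional split, the regional NIVL shares, the size of any deficit, and the number and size of site groups. The NIVL shares in Table 1.3-1 are whole-trial scenarios, not regional ones.

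**1. The plan's own figures.** The SAP states no error rate or power for the poolability tests. Its related figures reproduce:
- 0.45×83% + 0.55×67% = 37.35% + 36.85% = 74.2%, the 74% performance goal.
- An exact binomial test of 70% against 80% at one-sided 0.05 first reaches 85% power at n = 138 (power 85.1%, actual level 0.0466).

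**2. Shift due to mix.** With NIVL share m and no region effect, a region's patency is 0.77 + 0.16m. The crude regional difference is therefore 0.16 × (difference in m): 1.6 points for a 10-point gap, 3.2 for 20 and 6.4 for 40.

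**3. Hand check at 55% versus 35% NIVL, 90 versus 48 subjects.** Let d be the crude difference, se its standard error and c = 1.44 (two-sided 0.15). Then P(flag) ≈ Φ(d/se − c) + Φ(−d/se − c).
- *No region effect.* Patency is 0.858 and 0.826, so d = 0.032. se = √(0.858×0.142/90 + 0.826×0.174/48) = 0.0659, and d/se = 0.485. P(flag) = 0.170 + 0.027 = 0.197.
- *High-NIVL region 10 points worse in both groups.* Patency is 0.758 and 0.826, so d = −0.068. se = 0.0709, and d/se = −0.959. P(flag) = 0.008 + 0.315 = 0.32.

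**4. Simulation (40,000 runs per setting, 90 versus 48, the 90-subject region having the higher NIVL share).** Each cell gives the flag rate of the unadjusted likelihood-ratio test / logistic model with a PTS/NIVL term / Cochran-Mantel-Haenszel (CMH) test stratified by PTS/NIVL.

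| NIVL share | No region effect | High-NIVL region −10 points | Low-NIVL region −10 points |
|---|---|---|---|
| 50% v 40% | 16.3 / 15.6 / 15.0% | 39.6 / 48.6 / 46.9% | 56.8 / 49.8 / 50.0% |
| 55% v 35% | 19.7 / 15.7 / 15.1% | 32.1 / 47.6 / 46.0% | 65.1 / 48.4 / 48.5% |
| 60% v 20% | 32.5 / 15.6 / 15.1% | 20.1 / 42.7 / 41.5% | 79.2 / 44.2 / 44.1% |

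At equal mix (45% in both) the rates are 15.0 / 15.6 / 15.0% with no effect and 48.4 / 49.4 / 47.8% with the larger region 10 points worse, so adjustment costs almost nothing there. Across regional splits from 50:50 to 70:30 and N of 138 to 170, the unadjusted no-effect rate is 16-17% at 50/40 and 19-21% at 55/35.

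**5. Sites, no site effect, patency about 80-84%.** Rates of flagging at p<0.15:

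| Groups | Likelihood-ratio | Wald | Score |
|---|---|---|---|
| 14 of 10 | 28% | 0-0.2% | 14% |
| 12 of 12 | 26% | 0.2% | 14% |
| 8 of 17 | 22% | not run | 14-15% |
| 6 of 24 | 19% | 6% | about 15% |
| 4 of 35 | 17% | 10% | about 15% |

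With 10 groups of 17 the Wald rate is 1-4%. Wald fails with small groups because some group often has 100% patency (80% of runs at 12 groups of 12), which inflates its standard error. Case mix adds little here: letting NIVL share range over 20-60% across 12 groups of 12 moves the score test only from 14% to 16%.

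**The case against.** The strongest reply is that nothing is decided by these tests. A flag leads only to exploration, and screening the crude difference first and explaining it second is a coherent plan. A poolability review may also want to see real case-mix differences. All of this stands, and it disposes of the false-flag half of the concern. It does not answer the masked deficit, because the exploration starts only after a flag.

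Masking needs three things together: a marked gap in mix, a true deficit within the disease groups, and that deficit in the high-NIVL region. With the deficit in the low-NIVL region, the unadjusted test flags more often (65% against 48% at 55/35), though part of that excess is case mix. Adjustment still misses more than half of such 10-point deficits in the high-NIVL region. These limits stand and keep the point small.

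A reader might infer more than the documents support:
- *That the primary result is biased or depends on poolability.* The primary Z already weights the two groups, and section 1.2.4 blocks nothing.
- *That the regions do differ in mix.* The documents do not say. The 60% versus 20% row is illustrative only.
- *That the SAP rules out a PTS/NIVL term.* Its wording names geography without excluding other terms.
- *That the site test is known to miss its 15% level.* No statistic has been chosen. A score test roughly holds the level, and with 4-6 large groups the likelihood-ratio rate is only about 16-19%.

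**Conclusion.** The concern holds as a minor, inexpensive improvement. On the SAP's own 93% and 77%, the unadjusted regional flag picks up case mix once regional NIVL shares differ by about 20 points or more. At 55% versus 35% it fires about 20% of the time with no region effect, and it detects a 10-point deficit in the high-NIVL region about 32% of the time, against 46% with a CMH test. At a 10-point gap the no-effect rate is about 16% against 15%, which is negligible. These figures rest on the assumed 90/48 split, the assumed regional mixes and an equal deficit in both groups.

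For sites, the supportable point is that the statistic is unspecified. With many groups of about 10-17 subjects, a likelihood-ratio test would flag about 22-28% of the time with no site effect and a Wald test would rarely flag, against about 14-15% for a score test. How much this matters depends on the final number and size of the groups, which the documents do not fix.

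**What to change.** In section 1.2.4, add PTS/NIVL as a term in the geography logistic model, or use a CMH test stratified by PTS/NIVL. Keep the 0.15 level and report the unadjusted result as descriptive. For sites, state that the effect on patency will be judged by a score test; a stratified permutation test is not needed.

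This takes one or two sentences. It needs no new data, because the primary test already requires each subject's disease group. The downside is slightly more analysis.
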